#### Healthcare worker consent:

Healthcare workers (nurses and midwives) who care for patients receiving bCPAP therapy with or without blending in the Kiwoko unit will be approached to participate in the study by research personnel who are not in a supervisory position to the worker.

Risks as well as benefits and alternatives to study participation will be discussed. Consent forms will include a contact of the Makerere IRB chairperson. Consent will be documented with signature. Consent will be obtained for obtaining photographs, video or audio recording of the healthcare worker or they may decline this.

Healthcare personnel will have access to the country principal investigator (PI) to ask further questions. The health care worker can withdraw from the study at any time during or after the study is complete.

### **5.9.2 Confidentiality**

All subjects' confidentiality will be protected by not including names in data forms nor any personal identifiers in study report. Each participant will be assigned a study number and this linkage list/key will be kept separately from study forms, stored in a locked cabinet in a hospital office. The study code that links the study number to each participant will be destroyed immediately upon determination that the data set is final and locked.

- Study subjects (nor their parents/guardians) will not be contacted after the study for any reason.
- Paper data collection forms will be accessible only to the data collectors, data entry team, [medical monitors safety monitoring committee](#) and principal investigators. They will be stored in a locked cabinet in a hospital office. They will be maintained indefinitely after the completion of the study by Adara Development as long as secure storage is available.
- Video or audio recording of patients and/or healthcare worker observations and interviews will be maintained on the recording device which will be stored in a locked cabinet in a hospital office. The files will be uploaded to a password protected Adara server.
- Database software (REDCap [38]) will be maintained on the Adara server and password protected—only accessible by the data entry personnel, PIs, database designer, and biostatisticians/ data analysis team. These de-identified electronic databases may be maintained after the study time period per usual practices in password-protected database based at Adara.
- Funding recipients of Grand Challenges Canada (the sponsor of this study) must deposit data arising from Grand Challenges Canada-funded research into open access repository. All data in the repository will not include any personal identifiable information.

### 5.9.3 Risks, risk mitigation and adverse event reporting

Participation in this study does not raise the underlying risk associated with neonatal respiratory failure necessitating bCPAP therapy (i.e., death, disability, lung disease) in a resource-constrained setting. The rate of complications of the PATH bCPAP kit with blender should not differ from other improvised bCPAP kits as recommended by WHO. The baseline mortality for patients treated with bCPAP therapy in the Kiwoko Unit is 34%[35]. Most complications of bCPAP therapy are mild and can be addressed through careful bedside nursing management.[39]

#### **Mild Physical Risks:**

- Nasal irritation: A bCPAP system uses a nasal cannula as the patient interface. It is important that the cannula have a close fit in the nasal openings to prevent any loss of pressure. Multiple sizes of cannula are provided in the PATH kit to allow proper sizing for each patient. There is a risk of skin irritation from the nasal cannula due to rubbing or pressure from the cannula on surrounding areas. Standard of care for a patient on bCPAP therapy includes skin assessments every 3 hours. Proper sizing and positioning of the cannula, along with diligent skin care can prevent this complication.
- Abdominal distention: The bCPAP system works by administering a gentle flow of pressure into the infant's lungs to help them breath. An unavoidable but mild complication results from the flow of pressure that also enters the oesophagus and into the stomach. Accumulation of air in the stomach can lead to mild distention of the abdomen. An orogastric tube inserted into the patient's stomach and attached to an empty syringe (no plunger) will help eliminate any accumulated air. Positioning the patient to rest in a prone position can also help with abdominal distention.

**Moderate Physical Risks:**

- Nasal skin breakdown: With extended use, irritated skin surrounding the nasal openings may breakdown. Care includes diligent skin care and close observation. As tolerated, short breaks may be used to allow the skin time to heal. Discontinuation of bCPAP therapy may be an option if the infant's condition allows. This complication can be avoided with frequent assessment, proper sizing and positioning of the cannula, along with diligent skin care.
- Feeding intolerance: Accumulation of air in the stomach and intestines can lead to feeding intolerance (decreased digestion of milk, vomiting). Ensuring proper placement of the orogastric tube will help decrease this complication. The patient should receive a thorough examination to rule out other abdominal pathology that might be causing the distention. Smaller, more frequent feedings and placing the prone can also help to improve tolerance of feedings.

**Severe Physical Risks:**

- Hypoxia/hyperoxia: All use of oxygen poses a risk of hyperoxia when the amount delivered is higher than required. Blending oxygen with air provides the ability to administer levels of oxygen less than 100%. This poses a risk of hypoxia, when the percentage of oxygen administered is less than the patient requires. However blended oxygen is the only safe way to administer oxygen per WHO guidelines.[7] Risk of both hyperoxia and hypoxia is reduced by closely monitoring the patient's oxygen saturations via pulse oximetry. All patients enrolled in the study will receive continuous monitoring by pulse oximetry.
- Pneumothorax: Pneumothorax (reported rate of pneumothorax with bCPAP therapy in high resource settings in the literatures is 1.9%).[39] This can be life-threatening, but often can be treated with needle decompression, as is the standard of care at Kiwoko.[39] Early identification and prompt intervention are important to decrease risks of this complication. Refresher training will include assessment, identification and treatment for pneumothorax.

There is no psychological, social nor economic risk to the patient nor family with study participation when compared to standard of care in the unit.

There is no psychological, social nor economic risk to healthcare workers that participate in this study.

**Risk Mitigation**

The Kiwoko Hospital newborn care unit has been providing bCPAP therapy since 2012. The nursing staff are knowledgeable and experienced in the care of the patient receiving bCPAP therapy. Additional refresher training will take place before the study to ensure standardization of care. Patients will be closely monitored around the clock for complications of bCPAP use. Given need to titrate oxygen to saturations, patients will be monitored via continuous pulse oximetry.

**Table 14: Adverse Events and Mitigation of Risk**

Event	Mitigation
Mild adverse events:	
Nasal irritation	
 
• Provide diligent skin care
 
• Ensure proper fit, size, and position of cannula, add padding when indicated
 

Abdominal distention	
 
• Ensure orogastric tube is allowing accumulated air in the stomach to be vented between feeds
 
• Position infant prone
 

• Moderate adverse events:	
Nasal breakdown	
 
• Provide diligent skin care
 
• Ensure proper fit, size, and position of cannula, add padding when indicated
 
• Consider short time periods off bCPAP if tolerated or discontinue bCPAP therapy if appropriate
 

Feeding intolerance	
 
• Exam/review to screen for abdominal pathology
 
• Ensure orogastric tube is allowing accumulated air in the stomach to be vented between feeds
 
• Consider adjusting feeding volume or timing
 
• Position infant prone
 

• Serious adverse events:	
Hypoxia/Hyperoxia	
 
• Continuous monitoring with pulse oximetry
 
• Adjustment of oxygen concentration according to patient need
 

Pneumothorax	
 
• Early identification (diagnosed by sudden deterioration, unilateral loss of breath sounds, bedside X-ray or ultrasound as available)
 
• Needle thoracentesis
 

Death (34% expected mortality rate on bCPAP at Kiwoko)	

### **Care for injury**

If a baby has an injury or illness from the study device or the procedures required for this study, the reasonable medical expenses required to treat such injury or illness will be paid for by Adara, Kiwoko, PATH or another relevant party who is involved in conducting the investigation (collectively referred to as the Study Collaborator/s). Free medical treatment will be provided at Kiwoko Hospital for any trial-related injuries, as determined by the Primary Investigator and Study Collaborators of the Study. If necessary, the costs of referral and management of an illness will be also be paid for.

The coverage for such injury or illness is only available if the principal investigator and the Study Collaborators, where relevant, have decided that the injury/illness is directly related to

the device or procedures and is not the result of a pre-existing condition or the normal progression of the baby's medical condition. In particular, the independent medical monitorsafety monitoring committee will be involved in the determination of whether an injury in a study participant is related to study procedures or device (and not the underlying infant's health condition).

### **Adverse Event Reporting**

The standard of care will be followed as with any complications that results from/are associated with bCPAP use. Complications can be reported on the "HCW Observation of bCPAP Set-Up With or Without Blenders" form or the "Patient Data Form 2—Clinical Course and bCPAP Settings" and then will be reported on the adverse event record as described below.

Adverse events will be recorded on Adverse Event Record (Appendix D) and be treated as follows:

- **Mild Adverse Events:** assessed and followed by study personnel, treated by nurses and closely monitored until resolved.
- **Moderate adverse events:** assessed and addressed by country PI, monitored closely until resolution, recorded and reported to the IRB (as required) as well as notifying ~~medical monitor~~ the safety monitoring committee within 72 hours.
- **Serious adverse events:** assessed and addressed by country PI, monitored closely until resolution, recorded and reported to the IRB (as required) as well as notifying ~~medical monitor~~ the safety monitoring committee within 24 hours.

In addition, Unanticipated Adverse Device Effects (UADE) will be monitored and reported using the UADE Event Record (Appendix D). The USFDA defines a UADE as: "any serious adverse effect on health or safety or any life-threatening problem or death caused by, or associated with, a device, if that effect, problem, or death was not previously identified in nature, severity, or degree of incidence in the investigational plan or application (including a supplementary plan or application), or any other unanticipated serious problem associated with a device that relates to the rights, safety, or welfare of subjects".

### **Managing and reporting unanticipated problems or protocol deviations**

Unanticipated problems:

- Any breaches in confidentiality will be remedied immediately by the study team and reported to the country PI.
- Protocol deviations will be addressed by the country PI (to ensure the best care of the patient) and protocol deviations will be noted in the records for that patient.
- Changes at the site that affect the conduct of the research will be addressed by the study PI and, as necessary, reported to the Makerere IRB and PATH's Research Ethics Committee.

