## 5.0 CHAPTER FIVE: Methodology

### 5.1 Study design

This is an early feasibility study to evaluate the device's human interface and its impact on operator technique. As such, it is a limited clinical investigation. The study will help to obtain insights into: successful use of PATH's bCPAP kit with oxygen blenders, operator technique challenges, human factors (such as use errors and difficulties comprehending procedural steps) and patient characteristics that may impact device performance (anatomical limitations). The experience obtained from the study will be used to identify appropriate modification to the use procedures and/or the device as needed.

The study will take place in a newborn care unit at Kiwoko hospital, Uganda with experience using bCPAP and blended oxygen. It will use mixed methods, employing both quantitative and qualitative approaches. We will conduct prospective data collection of the usability and acceptability of the PATH bCPAP kit with oxygen blenders through observation of and in-depth interviews with healthcare workers, as well as prospective data collection of the clinical characteristics and outcomes of patients treated with the kit and blenders.

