### 5.7.2 Tools

See “Data Collection Forms” in Appendix D, these include:

- Patient Data Form 1 (Demographics and Admission Clinical Data)
- Patient Data Form 2 (Clinical Course and bCPAP Settings)
- Concentrator FIO2 Output Form
- Newborn Unit Shift Form
- Adverse Event Record
- Unanticipated Adverse Device Effects (UADE) Event Record
- Healthcare Worker (HCW) Usability Form
- Healthcare Worker (HCW) Observation of bCPAP With or Without Blenders Set-up Form
- Healthcare Worker (HCW) Initial Interview Guide
- Healthcare Worker (HCW) Follow-Up Interview Guide

Data will be collected on the forms at the following timepoints:

Table 10. Patient Specific Data Collection Timing:

Form	Event					
	bCPAP initiation	Blender start or change	bCPAP pressure change	bCPAP stopped	Patient discharged/ deceased	Unanticipated Adverse Device Effect or Adverse Event
Healthcare Worker (HCW) Observation of bCPAP With or Without Blender Set-Up	X					
Patient Data Form 1 (Demographics)	X			X	X	

and Admission Clinical Data)						
Patient Data Form 2 (Clinical course and bCPAP settings)	X	X	X	X		
Adverse Event Record						X
Unanticipated Adverse Device Effects (UADE) Event Record						X

Table 11. Unit/Equipment Specific Data Collection Timing:

	Each Shift	Each Week
Newborn Unit Shift Form	X	
Concentrator FIO 2 Output Form		X

Table 12. Nursing Specific Data Collection Timing:

	With Each PATH bCPAP initiation	Initial Interview	Final Interview
HCW Initial Interview Guide		X	
HCW Follow-up Interview Guide			X
HCW Usability Form	X		

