### 5.8.2 Data analysis

Table 13 presents a summary of variables, data sources and analysis plan. We will evaluate operational feasibility by analysing the domains below; each domain uses information from mixed data sources. We will create an index measure for each domain, all of which will be weighted equally. We will sum these index measures to determine overall operational feasibility.

- Ease of correct use: Median set-up time, frequency of correct set up, time to change blender, types and frequencies of user errors, frequency of changes to blend provided per day, frequency of bCPAP level adjustment per day
- Integration into service delivery: Count of patients treated with PATH bCPAP, Frequency of blending via air compressor and PATH blenders, Frequency of known bCPAP complications
- Confirmation of device functionality: Median and IQR of: FIO2 administered by PATH blenders (determined by blender used and FIO2 provided by concentrator), level of bCPAP (and min/max), total air/oxygen flow to bCPAP device (subset)
- Concentrator output: Ability to determine FIO2 delivered to patient
- Device malfunction: Frequency of device malfunctions with and without adverse events

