**Table 13. Summary of Relevant Data Analysis for Study Objectives**

Objective	Variables	Source of Data	Statistical analysis
Objective 1: To assess the operational feasibility of using the PATH bCPAP kit including, when appropriate, in-line oxygen	Observed use of kit by HCWs including completion of set-up steps, time to set-up, description of difficulties	
 
• Healthcare Worker (HCW) Observation of bCPAP With or Without Blender Set-Up
 
	
We will determine frequency of various parameters/variables collected on the use and set-up of the kit
 
Mean, standard deviations, medians and interquartile ranges will be used for

blending on neonatal patients		
 
• Patient data form 2 (clinical course and bCPAP settings)
 
• Concentrator FIO2 output form
 
	continuous variables based on their distribution
Objective 2: To assess the usability of the PATH bCPAP kit with oxygen blenders by healthcare workers.	Scores of usability by healthcare workers about ease of device set-up, learning the device, difficulty of use satisfaction with device and desire for continued use.	
 
• HCW usability form
 
	
We will use frequency table to summarize the responses on the Likert scale.
 
A total score generated by summing 10 items. Means, standard deviations and ranges will be reported.

Objective 2: To assess acceptability of the PATH bCPAP kit with oxygen blenders by healthcare worker.	Themes from HCW interview questions about what is liked best, least about the PATH bCPAP and blenders, ease-of-use initially and over time, difficulty of use, adequacy of blends available, adequacy of training, what could be changed, would HCW continue to use the PATH kit with or without blenders if they were available after the study end?	
 
• HCW Initial Interview Guide
 
• HCW Follow-up Interview Guide
 
	Notes from in-depth interviews will transcribed and imported in NVivo software, analysed using content and thematic techniques (mainly inductive approach)

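### The only staff-technique form is scheduled at bCPAP initiation, so the user-error frequency in the feasibility index is likely to be weighted towards initial set-up

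*Combined protocol and SAP*

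**What the plan says.** Section 5.1 names "human factors (such as use errors and difficulties comprehending procedural steps" among the things the study should reveal, with a view to changing the use procedures or the device. Section 5.8.2 builds the operational feasibility index from equally weighted domains. The first, ease of correct use, includes "types and frequencies of user errors" and the time needed to change a blender. The same section says that "each domain uses information from mixed data sources".

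Table 13 describes the Objective 1 variable as "Observed use of kit by HCWs including completion of set-up steps, time to set-up, description of difficulties". Its sources are the staff observation form, Patient Data Form 2 and the concentrator output form.

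Table 10 in section 5.7.2 sets the timing. The row for "Healthcare Worker (HCW) Observation of bCPAP With or Without Blender Set-Up" has one mark, at bCPAP initiation. The row for "Patient Data Form 2 (Clinical Course and bCPAP Settings)" has four: initiation, start or change of a blender, pressure change, and stopping bCPAP.

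On departures from the protocol, section 5.9.3 says that the country PI addresses them and that "protocol deviations will be noted in the records for that patient".

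**The concern.** The user-error count belongs to a primary objective, and its main purpose is to show where staff go wrong with the device. Section 5.5 says the fixed-ratio blender option is the only new feature of the kit. It also says that some infants will be blended by both systems because compressors fail or become free. For these infants the blender may first be placed well after bCPAP begins, and any infant on a blender may be swapped between the 37% and 60% parts. These are the moments when the new feature is handled, yet the form that records staff technique is not scheduled for them.

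If errors are observed systematically only at initiation, the reported frequency mainly describes assembly of a circuit. By section 5.5's own account that circuit has the same components as the one the unit already uses. A low error rate could then be read as evidence that the blender is easy to use correctly, when blender handling was observed only in part.

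**Working it through.** The plan gives no error rate, denominator or target to reproduce, so the check is mainly a comparison of the relevant sections.

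1. **What is to be measured.** Section 5.8.2 lists user errors, time to change a blender, blend changes per day and pressure adjustments per day in one domain. Several of these can arise only after set-up.

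2. **What is to be observed.** Section 5.7 says staff are watched during both set-up and use. It promises staff data from all 15 cases in which the blender is used.

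3. **When technique is recorded.** Table 10 marks the observation form once, at initiation. The table has a column for starting or changing a blender, and this form is not marked there. Table 12 likewise ties the usability form to each initiation. An infant who starts on the compressor and moves to a blender on day 2 therefore has a blender case under section 5.7 but no scheduled observation of the blender being placed.

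4. **What else is recorded later.** Form 2 is due at blender and pressure changes, so those events are not lost. Its title refers to clinical course and settings, not to whether a step was done correctly. It is also triggered by events, so an omission, where nothing is changed, would not prompt it.

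5. **Whether any other tool is named.** Section 5.7.2 lists ten tools. By title, none is a log of use errors or deviations. Section 5.9.3 routes complications from the observation form and Form 2 to the adverse event record; no similar route is given for errors. Sections 5.5 and 5.9.5 have research assistants alert staff to an incorrect set-up, but the text does not say that the intercepted error is recorded.

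6. **Illustration of where handling falls.** Take the 3-day median bCPAP course from section 5.4 and count one set-up plus c blender or pressure changes per day. The share of handling events after set-up is 3c / (1 + 3c). The documents do not give c, so these values are assumptions:
   - c = 0: 0 / 1 = 0%
   - c = 1/3: 1 / 2 = 50%
   - c = 1: 3 / 4 = 75%
   - c = 2: 6 / 7 = 86%
   - c = 4: 12 / 13 = 92%

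These are shares of events outside the observation form's schedule. They are not shares of errors missed, because Form 2 is completed at the same events and may capture some errors.

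**The case against.** The strongest reply is that capture during use is planned. Form 2 is an Objective 1 source and is completed at blender and pressure changes. Section 5.7.1 places research assistants at the bedside around the clock. Section 5.7 speaks of observing use as well as set-up, and section 5.8.2 draws each domain on several sources. The forms in Appendix D are not in the text available, so Form 2 may contain an error field. This is also a descriptive early feasibility study with a purposeful sample size. All of this stands, and it limits the point. It shows intention and capacity, but no form or schedule is named for errors after set-up.

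Three stronger readings are tempting and should not be made.

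- A reader might infer from section 5.9.3 that errors in use are treated as deviations and go only to the patient's record. The section does not say only, and it does not class use errors as deviations. Section 5.5 leaves bCPAP care to unit guidelines and staff discretion, so a departure from Table 6 is not clearly a deviation at all.
- A reader might infer that most device use goes unrecorded, or that changes to procedures would rest on set-up alone. Form 2's schedule, the usability form and the initial and repeat interviews contradict that.
- A reader might divide observed set-ups by the three-hourly assessments in section 5.5 to size the gap. Those are patient and vital-sign checks, not blend decisions, so the ratio says nothing about missed errors.

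**Conclusion.** The point holds in a limited form. On the visible text, the only form on staff technique is scheduled at bCPAP initiation, while the index counts errors and blender-change times that can arise later. No tool is named for errors after set-up. Followed as written, the user-error frequency is likely to be weighted towards initial set-up and could make the kit look easier to use correctly than it is.

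The size cannot be estimated from the documents. The illustration runs from 0% to 92% of handling events after set-up, depending entirely on an assumed change rate.

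The conclusion rests on two assumptions: that the single mark in Table 10 belongs to the initiation column, and that Form 2 does not already record errors. If Form 2 has such a field, the gap narrows to naming it in the analysis plan and giving a denominator. The point does not undermine the study, but it affects a component of a primary result and is worth settling before enrolment.

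**What to change.** 1. In Table 10, also mark the observation form in the column for starting or changing a blender. This gives the time to change a blender a scheduled source too.
2. Have the research assistants log device-handling errors during use, including set-up errors they intercept, with type, time and blender in line. Keep these separate from deviations unrelated to the device and from permitted clinical discretion, so that the count stays interpretable.
3. In section 5.8.2, define user error and report errors per set-up, per blender start or change, and per day on PATH bCPAP.
4. Add the log to the sources in the Objective 1 row of Table 13. If Form 2 already holds this information, name the field there instead of creating a new log.

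The cost is small, since the observers are already at the bedside: a little more recording time and a probably higher reported error count.
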